## 4. PARTICIPANT POPULATION

### 4.1. Clinical Effectiveness Trial

#### 4.1.1. Number of Participants

A total of up to 240 participants will be enrolled at the three sites.

#### 4.1.3. Exclusion Criteria

Potential participants who meet *any* of the following exclusion criteria are not to be enrolled in this study.

- Prior SGB
- Allergy to amide local anesthetics (e.g., ropivacaine, bupivacaine)
- Pregnancy (evaluated by urine test pre-procedure)
- Current anticoagulant use
- History of a bleeding disorder
- Infection or mass at injection site
- Myocardial infarction within 6 months of procedure
- Phrenic or laryngeal nerve palsy (hoarseness)

- History of glaucoma
- History of schizophrenia, other psychotic disorder, bipolar disorder, or personality disorder (axis 2) as verified by medical record review by an Army Co-Investigator with access to medical records
- Moderate or severe traumatic brain injury as verified by medical record review by an Army Co-Investigator with access to medical records
- Symptoms of moderate to severe substance use disorder in past 30 days
- Suicidal ideation in the past 2 months, documented by the M.I.N.I.-Plus Suicidality Items
- Any ongoing other major life stressor or condition not listed here that the site Investigator believes clearly would place the participant at risk for injury or a poor outcome (including anniversary of the inciting event, pending divorce, undergoing medical board/retirement, undergoing UCMJ or pending legal administrative actions, significant illness in participant or family)

#### 4.2. Acceptability Study

##### 4.2.1. Number of Participants

A total of up to 193 participants across the 3 sites will be enrolled in the qualitative study. Participants will include up to 131 service members, up to 14 spouses of service members, and up to 48 providers. The expected allocation of participants by pay grade and subjective assessment of change is shown in **Table 2**. These numbers will be adjusted to proportionally reflect study participants.

**Table 2. Number of Participants in Qualitative Study**

		Total					
		Reporting Improvement		No Improvement		Total	
		Groups	Individuals	Groups	Individuals	Groups	Individuals
Service members							
	Lower enlisted	8	48	4	24	12	72
	NCOs	3	18	3	18	6	36
	Officers		6		3		9
Service member/ spouse interviews							
	Lower enlisted	6	12	6	12	12	24
	NCOs	1	2	1	2	2	4
Providers							
	Family Medicine					4	16
	Behavioral Health					4	16
	SGB Physicians					4	16
Total		18	86	14	59	44	193
	Service members						131

		Total					
		Reporting Improvement		No Improvement		Total	
		Groups	Individuals	Groups	Individuals	Groups	Individuals
	Spouses						14
	Providers						48

**4.2.2. Inclusion Criteria**

The following inclusion criteria apply to the qualitative study:

- Service members must have received at least one SGB and/or study procedure during the past three months at a participating study site (as a participant in the clinical effectiveness trial or outside of the study)
- For clinical trial participants, they must have indicated willingness to participate in the qualitative study when asked by the RC at baseline data collection
- For non-clinical trial participants, they must be active-duty status
- A service member/spouse dyad will consist of a service member meeting the above criterion and his/her spouse, when the spouse has responded to the fact sheet describing the study (**Appendix 19-5**, given to the service member at screening)
- Providers will be Behavioral Health or other (e.g., Family Medicine) clinicians who have referred or could potentially refer service members to the study, and physicians who administer SGBs.

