## PROTOCOL SYNOPSIS (CONTINUED)

---

Effectiveness Study Design:	Blinded, multi-center, randomized, sham-procedure-controlled
Number of Participants Planned:	240
Target Population:	active-duty service members
Duration of Study:	10 weeks
Diagnosis and Main Eligibility Criteria:	Participants with PCL-C score of 32 or higher All participants must have anticipated assignment to installation for at least 2 months and have been offered an A-level modality PTSD treatment (see section 4.1.2 for definition)
Study Procedures/Frequency:	CAPS-5 following screening (prior to week 0) and at week 8 Stellate ganglion block at weeks 0 and 2 PCL-5 and PCL-C at weeks 0, 2, 4, 6, and 8 M.I.N.I.-Plus Suicidality Items at screening and weeks 0, 2, 4, 6, and 8 K6 Scale at weeks 0, 2, 4, 6, and 8 SF-12, GAD-7, PHQ-9, AUDIT-C/AUDIT, pain scale at weeks 0, 4, and 8
Acceptability Objectives:	

• to assess participants' perceptions of stellate ganglion block in relation to other PTSD treatment options

• to inform communication with service members before, during, and after the procedure

Acceptability Study Design:	Qualitative study using focus groups, small group interviews, and individual interviews (both in person and over the phone).
Number of Participants Planned:	193
Target Population:	

• participants in effectiveness clinical trial and their spouses

• service members who have received SGB for PTSD symptoms at the participating study sites outside of the clinical trial and their spouse

• providers who have referred or could potentially refer patients for SGB for PTSD symptoms at the study sites

• clinicians who provide SGB for PTSD

Duration of Study:	no individual's participation will last more than 90 minutes
Main Eligibility Criteria:	

• participants in effectiveness clinical trial who received at least one intervention and initial follow-up within the prior three months

• service members who have received at least one SGB for PTSD symptoms at the study sites within the prior three months

• providers who have referred or could potentially refer service members for SGB for PTSD symptoms at the study sites

• providers who perform SGB for PTSD symptoms at the study sites

---

---

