
clinical decision-making; the clinician, however, is not to disclose the participant’s intervention information to anyone else.

Immediately following the procedure, the participant will be observed in the procedure suite prior to transport to the recovery area for assessment of potential complications that could require immediate intervention, according to local clinic policy. They then will be taken to the post-procedure recovery area, where monitoring of vital signs will continue under the supervision of the recovery nurse for 20 minutes or longer, as dictated by clinic policy and participant condition. The study RC will use metrics to assess for a Horner’s syndrome ([Section 6.3](#)). A successful block will be recognized by the RC and perhaps by the participant (although we are unaware of data pertaining to possible signs and symptoms from saline injection near the SG). The RC will not share outcome information with the physician or the participant. While we cannot completely prevent the possibility of inadvertent un-blinding of study participants who may be familiar with the significance of developing signs and symptoms of SGB, no implicit or explicit confirmation will be given to the participants by the research team. This is a limitation of the proposed study and indeed any study with participant-accessible outcomes following an intervention.

Study intervention will be administered at week 0 and at week 2.

Participants will be evaluated for PTSD symptomatology prior to week 0 and at 8 weeks using the Clinician-Administered PTSD Scale for DSM-5 (CAPS-5). They will complete the PTSD Checklist for DSM-5 (PCL-5), the PTSD Checklist – Civilian Version (PCL-C), and the M.I.N.I.-Plus Suicidality Items at 0, 2, 4, 6, and 8 weeks; they also will complete the M.I.N.I.-Plus items at screening. The SF-12, GAD-7, PHQ-9, K6, AUDIT-C/AUDIT, and a short pain scale will be completed at weeks 0, 4, and 8.

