### **3.2. Acceptability Study Design**

The qualitative study will use focus groups, small group interviews, and individual interviews to compile a range of perspectives on service members' decision-making processes and information needs related to SGB. Participants will include service members, spouses, and providers. Data collection will occur at each study site because attitudes conveyed by leadership and chain of command may vary across installation. Scheduling will be based on the accumulation of ample service members indicating an interest in participating.

Participating service members will have received at least one SGB and/or study procedure within the prior 3 months, although this interval may be expanded if necessary for recruitment into focus groups. Because all study staff (with the exception of the physicians administering the study intervention) are blind with respect to treatment status, participants will include participants from both active and sham procedure arms. To increase homogeneity within focus groups and avoid potential distress among participants who do not experience symptom relief, groups will be stratified based on positive versus neutral or negative subjective assessment of change at the 4-week assessment (see [Section 6.4.12](#)) or at the time of screening for the qualitative study. Because beliefs and attitudes related to behavioral health treatment are likely to vary according to pay grade, separate groups will be held for lower enlisted service members and NCOs. Officers, if available as participants, will be interviewed individually. Data collection will address perceived benefits and drawbacks of SGB and other treatment options for PTSD; information needs before, and during the procedure; and participants' description of the effects of the procedure.

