##### **6.4.1. CAPS-5**

The CAPS-5 will be repeated, again via phone interview, at approximately 8 weeks following the first SGB, in support of the primary objective.

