#### 6.5. Acceptability Study Procedures

##### 6.5.1. Participant Recruitment and Group Assignment

###### 6.5.1.1. Service Members

###### *Clinical Effectiveness Trial Participants*

All service members enrolled in the trial will be eligible for the qualitative study if they have received at least one SGB study procedure during the three months prior to qualitative data collection and if participation would not cause undue distress, as described below. During Baseline Assessment, the RC will describe the qualitative study, following the recruitment script included in **Appendix 19-3** and providing the Fact Sheet included as **Appendix 19-4**. The RC will keep a list of all service members who indicate willingness to participate in the qualitative study. Recruitment for actual qualitative data collection will be determined by the

pace of accrual into the clinical trial. When qualitative data collection is scheduled, the RC will draw on this list to invite service members to participate in the qualitative study, either in the course of a follow-up visit or by email, following the scripts included as **Appendix 19-12**. Service members will not be contacted for qualitative study participation if the RC or treating provider considers that participation would cause undue distress based on their most recent contact with the individual.

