#### 9.1.3. After local IRB approval, the Protocol then must be submitted to HRPO for approval, which also must be documented before enrolling of participants may begin. ’ Informed Consent

##### 9.1.3.1. Effectiveness Clinical Trial

For the effectiveness clinical trial, it is the responsibility of the Investigator or his designee (e.g., the Research Coordinator) to obtain written informed consent from each individual participating in this study after adequate explanation of the aims, methods, objectives, and potential hazards of the study and prior to undertaking any study-related procedures. The discussion must take place in a private setting. The Investigator must utilize an IRB-approved consent form for documenting written informed consent. A model consent form is provided in **Appendix 20-1**. Each informed consent will be appropriately signed and dated by the participant and the person obtaining consent; all other pages of the consent are to be initialed by the participant, also. The informed consent form does not explicitly describe the Horner’s syndrome evaluations to be performed by the RC; they add no risk, and we do not wish to draw attention to this participant-observable phenomenon which may unblind the participant.

During the consent process it will be made clear to potential participants that if they indicate an intention to harm themselves or somebody else during the trial, their command will be notified. This includes verbal indications as well as those during online assessments, should relevant items be answered in such a way as to indicate emergent suicidal ideation. Those indicating emergent suicidal ideation during an online assessment (Section 6.4.13) will see a message on their screen recommending that they go to their nearest Emergency Department

(ED) for assistance. These individuals will also be asked to confirm (via checking a box on the screen) that they will not act on any suicidal thoughts before presenting to the ED.

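### Blinded trial participants may join acceptability focus groups about four weeks before their own week-8 CAPS-5, an avoidable route to unblinding

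*Protocol*

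**What the plan says.** The entry rule for service members appears three times in the protocol, and no version mentions week 8.

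- Section 4.2.2: "Service members must have received at least one SGB and/or study procedure during the past three months at a participating study site".
- Section 6.5.1.1: trial participants are eligible "if they have received at least one SGB study procedure during the three months prior to qualitative data collection".
- Synopsis: "participants in effectiveness clinical trial who received at least one intervention and initial follow-up within the prior three months".

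The only exclusion, in section 4.2.3, is undue distress. Section 1.2 describes the qualitative study as concurrent with the trial.

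On timing, section 3.1 states: "Study intervention will be administered at week 0 and at week 2". Section 6.4.1 repeats the CAPS-5 "at approximately 8 weeks following the first SGB, in support of the primary objective".

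On the sessions, sections 3.2 and 6.5.1.1 form groups by pay grade and by the change reported at week 4 or at qualitative screening. Both arms take part. Service members who had an SGB outside the trial are also eligible. Topics include participants' "description of the effects of the procedure". Trial participants may be invited "either in the course of a follow-up visit or by email".

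On protecting the blind, section 5.1 bars the coordinator from discussing Horner's syndrome with the participant. Section 9.1.3.1 leaves the coordinator's Horner's evaluations out of the consent form because "we do not wish to draw attention to this participant-observable phenomenon which may unblind the participant". Section 3.1 lets an outside clinician ask for a participant's assignment only once the week-8 instruments and second CAPS-5 are complete, and the participant stays blinded even then.

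**The concern.** The trial takes care to stop participants learning what their post-injection signs mean. The acceptability study then allows those same participants, while still awaiting their primary assessment, to sit in a group and compare what the procedure did to them. Some of those present may know they had a real block. A participant who noticed no signs could draw a conclusion about arm from what the others describe.

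The CAPS-5 interviewers are blinded, but they score the participant's own account of symptoms. A change in expectation can therefore reach the primary outcome, and also the week-6 and week-8 self-reports. The plan has no means of seeing it. Section 6.4.12 asks participants which procedure they think they had at week 4 only, and the self-assessment covariate in SAP section 8.6.1 can reflect nothing learned after that answer.

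**Working it through.** The plan gives no figure for early attendance or its effect, so there is none to reproduce. The check compares dates, in days from the first procedure.

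**Inputs**
- Procedures on days 0 and 14 (section 3.1).
- Final CAPS-5 at about week 8, day 56 (section 6.4.1).
- Follow-up windows run from 2 days before to 11 days after the nominal date (section 6.4). Week 4 opens on day 28 − 2 = 26, and week 8 closes on day 56 + 11 = 67. Applying the week-8 window to the CAPS-5 is my assumption.
- Three months taken as 91 days (my assumption).
- Table 2: 72 lower-enlisted and 36 NCO focus-group places, 9 officers, and 14 service members in spouse interviews.

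**Earliest seat in a group, relative to a day-56 CAPS-5**
- Grouping on the week-4 rating: 56 − 26 = 30 days before.
- Synopsis rule, with initial follow-up read as the week-2 window opening on day 14 − 2 = 12 (my reading): 56 − 12 = 44 days before.
- Literal rule in sections 4.2.2 and 6.5.1.1: 56 − 0 = 56 days before.

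The week-4 reading is the natural one for trial participants. The other two are eligibility floors.

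**Share of the eligible period that precedes the CAPS-5, week-4 reading**
- Eligibility ends on day 0 + 91 = 91 (first procedure only) or day 14 + 91 = 105 (both procedures).
- Both procedures: 30 / (105 − 26) = 30/79 = 38%.
- First only: 30 / (91 − 26) = 30/65 = 46%.

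**Ceiling on the number involved**
- 72 + 36 + 9 + 14 = 131, which matches the service-member total in Table 2.
- Focus-group places: 72 + 36 = 108, and 108/240 = 45%. This is reached only if every place goes to a trial participant. It counts as early exposure only if all of them also attend before week 8.

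**Window left if the CAPS-5 must come first**
- CAPS-5 on day 56: 91 − 56 = 35 to 105 − 56 = 49 days.
- CAPS-5 on day 67: 91 − 67 = 24 to 105 − 67 = 38 days.

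**The case against.** **Participants already hear about these signs.** Section 6.3 has the clinic nurse say at discharge that Horner's symptoms may occur for some hours, and section 3.1 concedes that inadvertent unblinding cannot be fully prevented. This stands, and it means that a focus group adds to the risk and is not its source. But being told that a sign may occur leaves its absence uninformative, whereas hearing several others describe it does not. The concession in section 3.1 covers what cannot be prevented; a session the study itself organises can be timed.

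**The consent form.** A reader might infer that it omits Horner's syndrome altogether. Section 9.1.3.1 says only that the coordinator's evaluations are not explicitly described.

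**Timing.** A reader might infer that participants will be seated after one procedure, six weeks or more before the outcome. The documents do not support that as the expected case. Screening for the qualitative study is described in section 6.5.1.1 only for service members outside the trial, who have no week-4 assessment, so the alternative rating fits them best. Trial participants grouped at week 4 will normally have had both procedures.

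**Permitted, not planned.** Sessions depend on accrual and on enough interested people, and nothing schedules them before week 8. An invitation at a follow-up visit is not attendance. No text says that trial and non-trial members share a group, though none separates them.

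**Direction.** A reader might infer that the bias must favour SGB. That is plausible but not shown. Because groups are split by self-rated change, a sham participant who improved could have expectation reinforced among other improvers, which would pull towards no difference.

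**Material not seen.** The scripts, topic guides and focus-group consent forms are appendices not included in the text reviewed, and the revision history records requests that participants not discuss the study. A timing or moderator rule there cannot be excluded, but it would belong in the eligibility criteria.

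**Conclusion.** The point holds as a gap in the eligibility rule. As written, it allows blinded trial participants from both arms to discuss procedure effects together about four weeks before the primary outcome, against the protocol's own blinding measures and with no later question on belief about arm to detect it.

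The documents do not support more than that. They do not say how many would attend before week 8, so neither the size nor the direction of any bias can be computed. The 45% is a ceiling on focus-group places, not an estimate of exposure. The concern is confined to groups: spouse interviews involve one couple at a time and officers are to be interviewed individually, so neither brings participants together to compare effects.

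The conclusion assumes that no unseen appendix already sets a week-8 condition. It should be fixed, because the risk is avoidable and the remedy is small; the documents do not show that the primary result is compromised.

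**What to change.** Add one condition to protocol sections 3.2, 4.2.2 and 6.5.1.1 and to the synopsis: clinical-trial participants may attend a qualitative focus group only after completing the week-8 instruments and the second CAPS-5. Section 3.1 already uses this milestone for unblinding requests.

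The willingness list taken at baseline can stay, and so can invitations during follow-up, provided the session falls after week 8. Spouse-dyad and individual interviews need no such rule for this purpose.

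The cost is a shorter recruitment window: about 24 to 49 days remain for a CAPS-5 between days 56 and 67, in which groups must be matched on pay grade and self-rated change. Later interviews leave less. At 12 weeks (day 84), the cut-off in the SAP section 8.1 sensitivity analysis, 105 − 84 = 21 days remain after two procedures. Section 3.2 already allows the three-month interval to be expanded. The trial's sample size is unaffected.

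The SAP addenda are post-unblinding, so an amendment cannot change sessions already held. For those, compare each trial participant's session date with the date of the second CAPS-5, report how many attended first, and repeat the primary analysis without them. That analysis would be post hoc and descriptive, since attendance occurs after randomisation.

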**4.2.3. Exclusion Criteria**

Service members will be excluded from the qualitative study if participation would cause them undue distress, in the opinion of the RC or treating clinician.

## **5. STUDY DRUGS**

### **5.1. Randomization and Blinding**

Participants eligible for the study will be randomized to either the sham or active treatment. Randomization will be conducted using a permuted block design and stratified by site to ensure that the 2:1 active:sham ratio is achieved at each center.

The control will be a sham injection of saline near the SG. The physicians administering the intervention will perform be unblinded. However, all others involved in the trial (RC, participants, RTI study personnel, etc.) will be blind to the administered treatment, and the sole interaction of the participants with the treating physicians will be in the treatment suite (except as required for participant safety). Also, the RC will not discuss the post-procedure presence or absence of a Horner's syndrome with the Investigator or participant.

### **5.2. Description and Handling of Study Drug**

Ropivacaine hydrochloride 0.5% for injection is FDA approved for use in SGB. Sterile normal saline for injection also is commercially available. There will be site-specific protocols for drawing up the study drug; these will produce sufficient documentation to identify which participants received active or sham intervention.

#### **5.2.1. Formulation**

The sterile saline for injection and ropivacaine will be used as commercially formulated and approved.

